9.0 Vulnerable Populations

9.1 Vulnerable Populations:

- Children
- Pregnant women/Fetuses/Neonates
- Prisoners
- Adults lacking capacity to consent and/or adults with diminished capacity to consent, including, but not limited to, those with acute medical conditions, psychiatric disorders, neurologic disorders, developmental disorders, and behavioral disorders
- Approached for participation in research during a stressful situation such as emergency room setting, childbirth (labor), etc.
- Disadvantaged in the distribution of social goods and services such as income, housing, or healthcare
- Serious health condition for which there are no satisfactory standard treatments
- Fear of negative consequences for not participating in the research (e.g. institutionalization, deportation, disclosure of stigmatizing behavior)
- Any other circumstance/dynamic that could increase vulnerability to coercion or exploitation that might influence consent to research or decision to continue in research
- Undervalued or disenfranchised social group
- Members of the military
- Non-English speakers
- Those unable to read (illiterate)

PROTOCOL TITLE: Increased thalamocortical connectivity in tDCS-potentiated generalization of cognitive training

VERSION DATE: January 26, 2023

- Employees of the researcher
- Students of the researcher
- None of the above

9.2 Adults lacking capacity to consent and/or adults with diminished capacity (IQ 70-75) to consent: One of the hallmark features of psychotic illnesses is diminished cognitive functioning. To date, there are relatively few treatments available for cognitive deficit. This study is a minimal risk trial and those with diminished cognitive functioning will not face greater risks by participating. In fact, we are matching the cognition level of the healthy comparison group in Cohort 1 (IQ 70-115) to that of the SZ group in Cohort 2. This is being done so that both groups will have the headroom to improve with the intervention. All participants must have capacity to provide informed consent at enrollment and throughout the study. Please refer to section 20.5 for the procedures to determine capacity to consent.

9.3 Additional Safeguards:

This research project is examining a potential treatment for impaired cognition in psychotic illnesses (Cohort 2); therefore it is necessary to include individuals with diminished cognitive functioning to evaluate the effectiveness of the proposed therapy. Both Cohort 1 and Cohort 2 will have the same range of cognition (IQ 70-115). All participants must have capacity to provide informed consent at enrollment and throughout the study. Please refer to section 20.5 for the procedures to determine capacity to consent.

10.0 Local Number of Participants

10.1 Local Number of Participants to be Consented:

We anticipate screening 300 healthy controls in order to enroll 90 participants in Cohort 1. We anticipate screening 130 SZ Patients in order to enroll 90 participants in Cohort 2.

11.0 Local Recruitment Methods

11.1 Recruitment Process:

Cohort 1: Healthy community (HC) sample:

Advertisements and postings announcing the study will be placed in University newspapers, organizational and departmental newsletters, online, and in public places. Study staff or weblinks will direct volunteers to a HIPAA-compliant online portal (REDCap) with a thorough description of the requirements of the study, such as the 3-day per week training for 12 weeks, and will allow them to answer relevant screening questions, such as tDCS or MRI contraindications. This mechanism is maintained through the College of Liberal Arts and has already been used in IRB approved studies.

Cohort 2 Patients with schizophrenia or schizoaffective disorder (SZ) sample:

SZ volunteers will be recruited directly from Guild Incorporated community mental health agency and Fairview Riverside Adult Day Treatment Center. Both organizations have provided letters of support, which are attached in ETHOS. SZ volunteers will also be recruited through referrals from other researchers at the University of Minnesota and from community and mental health agencies, paper and online postings, and in-person and telephone announcements made to support and advocacy groups. Through a call or in-person meeting study staff will provide a thorough description of the requirements of the study for SZ volunteers. Interested SZ volunteers will be asked screening questions about demographics, likely diagnosis, MRI eligibility and cognitive ability.

Patients from the Fairview Riverside Adult Day Treatment Center will primarily learn about our study through an IRB-approved flyer posted on a board (IRB approved) placed on a hallway wall at their treatment program.

PROTOCOL TITLE: Increased thalamocortical connectivity in tDCS-potentiated generalization of cognitive training

VERSION DATE: January 26, 2023

They may also be told of the study by treatment program staff. If a patient is interested in participating in the study, they will be instructed to contact the study at a provided a study phone number or email address. Alternatively, we may provide a physical opt-in form (IRB approved) and instruct patients to return it with their name and signature to a locked box installed next to the flyer board. Only research staff have a key to access that locked box to ensure privacy, and will check the locked box regularly. Research staff will follow up with interested participants and set up a phone conversation or in-person meeting where the patient can learn more about the study and complete screening procedures.

All outpatients seen at the UMP Psychiatry Clinic are asked to complete a Consent to Contact for Research form to indicate if they are interested in being contacted for research opportunities. Study staff will request the contact information for those who have signed the consent form and meet basic inclusion criteria for the study, namely clinical diagnosis of a psychotic illness. Additionally, we have kept lists of previous participants or interested individuals who did not pass phone screens, who have consented to being contacted again in the future for further research opportunities. Individuals in both of these lists will be contacted by study staff, who will ask to describe the study to the individual on the phone and determine interest.

The Psychiatry Department has hired a Research Advocate who will be available to UMP clinic staff as a neutral party who can discuss research opportunities with patients. During a regularly scheduled clinic visit, the Research Advocate may briefly meet with the patient and ask them if they are interested in hearing about any research opportunities at the University of Minnesota. If the patient agrees, the Advocate will describe available studies which the patient may qualify for and if they are interested, provide contact information and recruitment materials to the patient. The Advocate may also ask if it would be okay to provide the patient's contact information to the study team or introduce them to study staff if they are available. The Advocate may also be responsible for asking patients to sign the consent form mentioned above which indicates if the patient may be contacted for research opportunities in the future.

Clinicians who see patients with psychotic illnesses within recruiting clinic locations may also discuss this study with their clients to see if they are interested in participating. If the client agrees, the provider may request that the client fill out a Consent to Contact for Research form, may ask to share their contact information with the study staff, or may provide them with IRB approved recruitment materials with contact information for the study.

The outpatient Psychiatry Clinic in the Department of Psychiatry & Behavioral Health at the University of Minnesota provides patients with the opportunity to indicate whether they are interested in being contacted to learn about research studies or whether they prefer to not be contacted. This is accomplished through provision of a secure electronic REDCap consent form. Access to the voluntary contact information is managed by the Department of Psychiatry & Behavioral Health and securely stored and accessed by the Institute for Health Informatics Data Warehouse (BPIC) at CTSI (UL1TR002494). The department's Research Recruitment Specialist partners with BPIC to request a registry database for specific, IRB approved studies. We are requesting permission to receive this contact information to recruit participants for study #STUDY00003506. We will only contact patients who have indicated an interest in hearing about research.

The Department of Psychiatry and Behavioral Sciences provides information about research opportunities for the public on a University of Minnesota webpage. Our study will be listed for public information and interest and include information about the study, including contact information, inclusion/exclusion criteria, IRB approval number, and purpose of study.

PROTOCOL TITLE: Increased thalamocortical connectivity in tDCS-potentiated generalization of cognitive training

VERSION DATE: January 26, 2023

The Research Recruitment and Outreach Specialist (RROS), employee of the Department of Psychiatry, describes research opportunities to patients and provides study contact information to interested individuals. Potential participants may also provide confidential contact information to the RROS for the study coordinators. We will use advertisements on digital media platforms to reach our research population via demographic (geographically central to study site) and key words. Clicking the link will bring them to a link them to the informative REDCap database.

We will be using ResearchMatch as an additional source of recruitment. ResearchMatch.org is a national electronic, web-based recruitment tool that was created through the Clinical & Translational Science Awards Consortium in 2009 and is maintained at Vanderbilt University Medical Center. Potential volunteers will be contacted using the IRB-approved website recruitment language. Volunteers will then have the option of replying yes or no through a set of quick links available in the notification. If a volunteer chooses to respond in the affirmative, they will authorize ResearchMatch to release their contact information to me and we will be responsible for managing that information according to institutional guidelines.

We will use Quick Response (QR) codes on all printed and digital materials which will direct potential participants HIPAA compliant registry in REDCap.

We will utilize the Consortium of Psychosis Research Recruitment (COPRR) in the Department of Psychiatry & Behavioral Sciences. COPRR provides research participants with the opportunity to be added to a registry that contains their demographic and contact information, some assessment results, and study participation updates. The goal of COPRR is to reduce participant burden by centralizing recruitment and sharing assessment data that is collected in most studies. Data is stored in a secure REDCap database. Access to the database is controlled by the department's Research Recruitment & Outreach Specialist and is only granted after sufficient approval is confirmed. We will only use COPRR for its intended purposes and will follow guidelines from the COPRR PI for use of the database.

Email Communication with Potential Participants and Consented Participants: Potential participants may communicate with the study via email throughout the recruitment process. After signing the consent form and entering the study, however, if participants wish to continue communicating via email they must opt-in by signing a "Guidelines and Consent for Unsecured Email Correspondence for Research Participants." This form notifies participants of the confidentiality risks entailed in using unsecured emails, documents their consent to use this form of communication, and instructs them as to how to withdraw their consent at a later time should they choose to do so.

11.2 Identification of Potential Participants:

Healthy Controls: Potential participants will self-identify in response to advertisements and postings.

SZ cohort: Potential participants will self-identify in response to advertisements and postings, as well as through referrals from other researchers at the University of Minnesota. Potential participants will also be identified directly from Guild Incorporated community mental health agency and Fairview Riverside Adult Day Treatment Center (letters of support are attached in ETHOS) and from community and mental health agencies.

11.3 Recruitment Materials:

- Flyer (paper and online versions)
- Posters, contact cards, and rackcards
- Mail ads
- Newspaper ads

PROTOCOL TITLE: Increased thalamocortical connectivity in tDCS-potentiated generalization of cognitive training

VERSION DATE: January 26, 2023

- Online portal (REDCap)
- Digital media ads
- QR codes linked to IRB approved contact portal
- Department of Psychiatry research opportunities website

11.4 Payment: subjects will be compensated according to the following schedule:

Baseline evaluation = \$30

Follow-up at 6 weeks = \$50

Follow-up at 12 weeks = \$75

Follow-up at 24 weeks = \$100

Intervention - 36 sessions (3 visits/week x 12 weeks) = up to \$396 if all sessions are completed (\$11 average per session)*

Attendance bonus = up to \$60**

3 scans = \$150

4 Motivation questionnaires (optional): \$40

Cognitive Effort Discounting Task (optional): \$0-5 per visit (x4 visits = maximum of \$20)

Total possible compensation = \$921

* Graded compensation for WM/tDCS sessions: Compensation for WM/tDCS sessions increases as a participant progress through the study. Sessions will be compensated at rates of \$8, \$10, \$12, and \$14 per visit. Payment tiers increase \$2 every 9 completed sessions (if a participant attends 9 sessions at a given rate payment will increase to the next tier). If a participant misses a session, the payment does not go up until they have completed 9 sessions at a given rate.

** Attendance bonus: Additionally, if a participant completes 3 sessions in a week, they will receive a \$5 attendance bonus for that week. Research staff will track participant attendance using a punch card and increase payment accordingly.

Participant travel and parking expenses: additional funds have been allocated in the budget to assist participants with travel and parking expenses on an as-needed basis. Participants will be informed in the consent form that these funds are available and to ask the research staff if they are interested in utilizing them.

Compensation for additional visits: Additional visits may be scheduled in order to recollect or finish collecting data (e.g. in the event that a standard study visit is disrupted by a technical issue such as equipment malfunction). In such cases, participants will be compensated for the additional time spent completing these study activities according to the following guidelines:

- For additional visits at involve assessment activities (activities normally completed at the Baseline or follow up visits at week 6, 12, or 24), participants will be compensated at a rate of \$15/hr.
- For additional visits that involve training session activities (activities normally completed at the tDCS + cognitive training sessions), participants will be compensated for a full training session at the rate corresponding to their progress through the graded compensation plan mentioned above. A participant must still complete 3 successful sessions at a given rate in order to progress to the next compensation tier.
- If a participant terminates a visit early resulting in incomplete data, their compensation for that visit may be prorated according to the time spent during that visit.

PROTOCOL TITLE: Increased thalamocortical connectivity in tDCS-potentiated generalization of cognitive training

VERSION DATE: January 26, 2023

- For other cases, compensation for additional visits or activities will be commensurate to the time and demands required of the participant for that visit/activity.
- An additional \$10 will be provided as compensation for CT scans to confirm clear orbits as an MRI safety measure. CT scans will only be offered as needed for participants who have a history of metalworking and cannot be cleared to safely proceed with an MRI scan unless we have documentation of no metal fragments in the eyes. Only these participants will complete a separate consent form addendum which includes information about the additional \$10 compensation.

13.0 Risks to Participants

13.1 Foreseeable Risks:

TDCS is considered to be a safe brain stimulation technique that rarely results in adverse events. The FDA has determined that it is a non significant risk device and consequently will not provide an IDE. There is currently no evidence of serious side-effects. Mild side-effects that typically resolve upon discontinuing tDCS include light itching or tingling under the electrode at the beginning of administration, skin redness, headache, fatigue, and nausea. A rare side effect of tDCS is a burn on the skin underneath the electrodes (less than 1 out of 500 sessions). The subject may choose to discontinue stimulation at any time during the session if experiencing excessive discomfort or side effects. Although seizures are not a known risk of tDCS intervention, anyone with a history or a risk for seizures will be excluded from the study. No other risks related to tDCS are anticipated.

PROTOCOL TITLE: Increased thalamocortical connectivity in tDCS-potentiated generalization of cognitive training

VERSION DATE: January 26, 2023

To minimize risks regarding tDCS, study staff will be using standards of administration that have been shown as safe in numerous other studies using transcranial direct current stimulation. The length of administration of the current, size of electrode sponges used, and method of applying stimulation are the same as methods of administration that have been demonstrated as safe.

The other potential risks pertain to the maintenance of confidentiality. Participants will be probed for personal information during the interviewing process. As noted in the consent form, participants will be told that all diagnostic and other sensitive raw data will be kept in a locked file or secure server and available only to authorized investigators involved in this study. To minimize confidentiality risks, as noted in the consent form, all diagnostic and other sensitive raw data will be kept in a locked file or secure server and be available only to authorized investigators involved in this study. Genetic and epigenetic information will be for research purposes only and will not be included in participants' medical records. Genetic specimens and data will be labeled with the participant's study ID number and will not contain personally identifying information. Participants may opt-in to communication via email by signing a form, "Guidelines and Consent for Unsecured Email Correspondence for Research Participants", notifying them that unsecured emails pose a risk to confidentiality.

MRI risks. Individuals will complete a screening questionnaire for contraindications of MRI scanning. Any affirmative responses on the questionnaire will result in an interview regarding the possible contraindication. An attempt will be made to secure any records of the nature of the possible contraindication and this information will be reviewed by the PI and/or CMRR staff at the University of Minnesota. A determination will be made regarding the level of risk to the subject and whether they are approved for scanning. If approved for scanning by professionals, all risks to the subject will be conveyed to him or her so they can deliberate as to whether or not they want to complete the procedure. Any concerns from the review committee will be conveyed to the participant at that time. If the subject is not approved for scanning, the subject may not have the scan and will be excluded from that part of the study.

There are no known risks to humans due to the static magnetic field. Subjects, operators, and guests are carefully screened prior to entering the magnetic environment, and frequently reminded of the potential danger of introducing magnetic objects to the controlled area. Subjects are carefully screened and excluded from the study if they have any implanted devices. Subjects are always accompanied when near the magnet, and reminded to move slowly and carefully as they enter and leave the magnet.

The risk of tissue damage by energy emitted by the MRI device is controlled by compliance with FDA guidelines for commercial MRI devices. Safety devices are in place so that the magnet will cease to operate should any parameters begin to exceed their preset safety limits. The risk of peripheral nerve stimulation by dB/dt is limited by safety devices. The noise levels generated by each scan are monitored to ensure adherence to guidelines. In addition, subjects are provided with earplugs and secondary protection (foam covering or headphones) to increase comfort during the scan.

CT Risks. If a participant is suspected to have metal in their body and undergoes a CT scan, the CT scan involves exposure to ionizing radiation in the form of x-rays. Everyone receives a small amount of unavoidable radiation each year from space and from naturally occurring radioactive materials in the environment. The amount of radiation exposure received from a CT scan varies according to the size of the patient and the portion of the body that is scanned. The low dose CT scan performed for this study gives the body the equivalent of about 1 year or less of natural background radiation. The radiation discussed here does not include any exposure a participant might receive from their regular medical care. Generally, at such low radiation exposures, scientists disagree about the amount of risk and there may be no extra risk at all.

PROTOCOL TITLE: Increased thalamocortical connectivity in tDCS-potentiated generalization of cognitive

training

VERSION DATE: January 26, 2023

13.2 Reproduction Risks:

Since the MRI risks to fetuses are unknown, pregnant women are excluded from the study. The radiation from a CT scan may involve risks to an infant, embryo, fetus, or nursing infant which are not known at this time.

Female subjects in child-bearing years are asked to confirm they are not pregnant.

13.3 Risks to Others: N/A

14.0 Potential Benefits to Participants

14.1 Potential Benefits: There is no guarantee of direct benefit to subjects.

15.0 Statistical Considerations

15.1 Data Analysis Plan:

Analyses to test SA1, whether ipsilateral thalamocortical (prefrontal) FC changes are affected by hemisphere, length of treatment or modeled dosage will be conducted separately for Studies 1 and 2. We will use FSL Randomise (“Randomise/UserGuide - FslWiki,” n.d.) using non-parametric thresholding (5000 permutations, p-value 0.001) to avoid inflated false positive rates (Eklund, Nichols, & Knutsson, 2016), and threshold for significance using threshold free cluster enhancement (TFCE). Randomise design matrix files and contrast files (“GLM - FslWiki,” n.d.) will model specific contrasts to compare the effect of right v. left active-tDCS or sham on thalamo-prefrontal FC. Main effects of hemisphere (right active-tDCS vs left active-tDCS and sham-tDCS H1.1), length of treatment (H1.2), and modeled dosage (H1.3) will be examined for each fMRI dataset (rest, N-Back, and DPX). Group x Time (pre-intervention, mid-intervention, post-intervention) interactions will also be examined for each fMRI dataset. In addition to motion correction and motion-related artifact removal, 24-parameter motion estimates will be included as regressors of noninterest (Power, Schlaggar, & Petersen, 2015). Rest. Rest will provide the most straightforward use of the regressor, which is to detect whether changes in thalamocortical connectivity exists. Since this test is in the absence of particular task demands any changes noted suggest trait-related functional connectivity changes. N-Back. Task-dependent connectivity associated with N-back task performance will be identified by modeling the block task design together with the thalamic regressor (similar to psychophysiological interaction (PPI) analysis (Friston et al., 1997)). Blocked fMRI analysis will allow us the best power to detect hemodynamic changes within brain networks related to working memory. The primary analysis for the N-Back tasks will consider the 2-back conditions alone. Subsequent analyses will examine the 2 > 0-back contrast to strengthen interpretation of any observed changes in task-dependent thalamocortical connectivity. DPX. Task-dependent connectivity associated with the DPX task demands will be identified by analyzing cue and probe events together with the thalamic regressor. Preliminary analysis for the DPX task will examine B-cue related connectivity alone, as this draws the most on proactive, WM-dependent, control. Subsequent analyses will strengthen interpretation by examining both B-cue > A-cue related connectivity, as well as connectivity changes associated with response-related, or reactive, control (during the AY condition). These analyses can all be completed before the blind is broken, with direction of any effects to be resolved after breaking the blind.

Analyses to test SA2, that generalization and durability are driven by right tDCS more than left tDCS or sham (H2.1), longer treatment length (H2.2) and higher modeled dosage (H2.3) will be conducted both between and within groups (for both Studies 1 and 2). The first step will establish the existence of between-group training effects using repeated-measures ANOVA’s on the key performance outcome variables (d' scores for the word and picture N-backs, d'-context for the DPX, and the composite score for MCCB). We will also evaluate differences in self-rated engagement and experimenter-rated Work Behavior Inventory (Bryson et al., 1997), sleep patterns, age, baseline IQ, and these will be used as covariates of non-interest as appropriate.

PROTOCOL TITLE: Increased thalamocortical connectivity in tDCS-potentiated generalization of cognitive

training

VERSION DATE: January 26, 2023

To examine SA3, the relationship between thalamocortical FC change and generalization and durability, we will examine the nonparametric relationships between changes in thalamocortical connectivity and improvements on the trained task (word N-back d'), proximal transfer (picture N-back d'), and more distal generalization (DPX d', MCCB composite score) and durability (H3.1 and H3.2 respectively). If analysis of covariates suggest that there are important sources of within-group variance in learning (e.g. age, baseline IQ, etc.), then hierarchical regressions will be used on Fisher's transformed z-scores of thalamocortical connectivity. In addition, to determine whether thalamocortical FC changes predict stability in learning and generalization, task performance at 24 weeks will also be subjected to hierarchical regressions. The regression model will enter covariates on step 1, and thalamocortical connectivity on step 2. The statistician will be blind to condition until analyses are completed.

In all cases, these relationships will be tested separately for Cohort 1 and Cohort 2, as changes associated with improvement are likely to be different for groups with different mean levels of ability. Follow-up analyses will determine the extent to which these observed differences suggest actual differences between these populations. However, the current study is not designed to directly compare the populations.

15.2 Power Analysis:

75 completers in cohort 1 and cohort 2 will provide power of .80 to detect effects as small as $\eta^2=.03$ for key confirmatory analyses (tested at $\alpha = .05$) and $\eta^2=.05$ for other analyses (tested at $\alpha=.005$), with nearly as strong power for the analysis of the 24 week follow-up. The more conservative approach of intent-to-treat analysis ($n=90$) will also be conducted for Cohort 2, for which the study will be sensitive to $\eta^2=.027$ (tested at $\alpha = .05$) and $\eta^2=.042$ (tested at $\alpha = .005$). These effect sizes are much smaller than the group x time effect for generalization as measured by the MCCB in our pilot tDCS data ($\eta^2=.08$), suggesting the proposed study is well-powered. While power analyses for neuroimaging studies are challenging due to the interactions of voxelwise-thresholds, brain-wise error correction and spatial smoothness, the proposed studies will be well-powered to detect group x time voxel differences as small as $\eta^2=0.07$ (tested at $\alpha = .001$), and in any case the samples are twice the size of our previous, successfully replicated, neuroimaging studies of brain change following cognitive remediation. Within-group responder analyses conducted for completers ($n=25$ per cell) will have power of .80 to detect correlations $r \geq .34$, a lower magnitude than we already observed ($r=.55$).

15.3 Statistical Analysis:

See section 16.1

15.4 Data Integrity:

The investigator is responsible for ensuring the accuracy, completeness, legibility, and timeliness of the data reported. To enhance scientific rigor, avoid bias and enhance reproducibility, our triple-blind randomized design will use a stratified permuted block randomization procedure (Matts & Lachin, 1988) to roughly equate age and baseline WM performance across groups with a block size of 6. Neither participants nor experimenters will know group assignment. TDCS software programming will allow staff to randomly select one of the three hemisphere conditions (right, left, sham) corresponding to eight letters (six to be distributed evenly among three conditions for HCs, two to be distributed evenly among two conditions for SZs) encoded to preserve the blind. Randomization will be facilitated and the blinding code will be maintained by the study statistician.

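### With 5000 permutations, an imaging result judged at p = .001 depends partly on the random seed when the true p lies between about .0005 and .002; section 15.1 should use more permutations and say what the .001 refers to

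*Combined protocol and SAP*

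**What the plan says.** Section 3.1 lists SA1, the effect of stimulation on thalamocortical connectivity, first among the primary outcomes. Section 15.1 tests it with FSL Randomise, using "non-parametric thresholding (5000 permutations, p-value 0.001) to avoid inflated false positive rates". The same sentence goes on to "threshold for significance using threshold free cluster enhancement (TFCE"). It does not say whether .001 is a voxelwise level or the level for TFCE family-wise-corrected p-values, and it gives no other significance level for imaging. No random seed is mentioned. The rule covers the effects of hemisphere, length of treatment and modeled dosage in each fMRI dataset (rest, N-back, DPX), separately by cohort; in addition, "Group x Time (pre-intervention, mid-intervention, post-intervention) interactions will also be examined for each fMRI dataset".

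Section 15.2 claims adequate power for "group x time voxel differences as small as $\eta^2=0.07$ (tested at $\alpha = .001"). That claim is introduced by a caveat: "While power analyses for neuroimaging studies are challenging due to the interactions of voxelwise-thresholds, brain-wise error correction and spatial smoothness". The sample behind section 15.2 is 75 completers per cohort, in cells of 25.

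**The concern.** A permutation p-value is a count divided by the number of permutations. Near .001, with 5000 permutations, the count is about 5, and a count of 5 is a noisy basis for placing a result on one side of a line. Two analysts with the same data, model and plan but different seeds could reach different conclusions on a contrast for the first-listed aim. Section 15.4 names reproducibility as a purpose of the design, so this is worth closing.

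A second and separate point is that the imaging sensitivity in section 15.2 refers to a single voxel at alpha .001, whereas significance under section 15.1 is to be declared by TFCE. A reader could take the .07 as the power of the planned test.

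**Working it through.** **Inputs.** Number of permutations B = 5000 and level .001 (section 15.1). Eta-squared .07 at alpha .001, 75 completers, 25 per cell and target power .80 (section 15.2; the .80 is stated for the non-imaging analyses and assumed to carry over).

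**1. What p ≤ .001 requires.** Let b be the number of permuted statistics that reach the observed one. Counting the observed labelling, p = (b + 1)/(B + 1).
- B = 5000: b + 1 ≤ .001 × 5001 = 5.001, so b ≤ 4.
- B = 50,000: b + 1 ≤ .001 × 50,001 = 50.001, so b ≤ 49.

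**2. Monte Carlo error at a true p of .001.** SE = sqrt(p(1 − p)/B).
- B = 5000: sqrt(.001 × .999/5000) = .00045, or 45% of p. The expected count is 5 and the exact 95% range of the count is 1 to 10, which as a proportion of 5000 is .0002 to .0020.
- B = 50,000: SE = .00014. The exact 95% range of the count is 37 to 64, or about .0007 to .0013.

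**3. Chance that a run declares p ≤ .001.** b is binomial(B, true p). The entries are P(b ≤ 4) and P(b ≤ 49).

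| True p | B = 5000 | B = 50,000 |
|---|---|---|
| .0003 | 98% | >99% |
| .0005 | 89% | >99% |
| .0007 | 73% (missed 27.5%) | 99% (missed 1.0%) |
| .0010 | 44% | 48% |
| .0013 | 22.4% | 2.3% |
| .0015 | 13% | 0.1% |
| .0020 | 3% | <0.1% |

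Two independent runs disagree with probability 2d(1 − d), where d is the chance of declaring. At a true p of .0007 and B = 5000 this is 2 × .725 × .275 = 40%. At B = 50,000 it is 2 × .990 × .010 = 2%.

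**4. If the decision level is family-wise .05 instead** (an assumption; the plan does not say so). SE = sqrt(.05 × .95/5000) = .0031, about 6% of p, with a 95% range of .044 to .056. At that level 5000 permutations is adequate.

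**5. Permutations needed at .001.** For a relative SE of c, B = (1 − p)/(p c²). For c = 20%: .999/(.001 × .04) = 24,975. For c = 10%: .999/(.001 × .01) = 99,900.

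**6. What the .07 in section 15.2 represents.** I used a noncentral F for group × time with k arms and m times: f² = η²/(1 − η²), λ = f² × N × m/(1 − ρ), df = (k − 1)(m − 1) and (N − k)(m − 1). The within-subject correlation ρ is not in the documents; I assumed .5. With k = 3, m = 2, N = 75 and η² = .07: f² = .07/.93 = .0753, λ = .0753 × 75 × 2/.5 = 22.6, df = 2 and 72. Power at alpha .001 is .82, and 80% power is reached at η² = .0674, which rounds to the stated .07. This agreement depends on the assumptions: at ρ = 0 power is .36; with three times it is .95; with two arms and two times it is .90. The figure is therefore recovered to its printed precision by a single-voxel test with no brain-wise correction, under one plausible set of inputs.

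As a rough indication only, a Bonferroni correction over an assumed 50 to 1000 independent tests gives power at .07 of .82 to .54 for family-wise .05, and about .44 to .20 for family-wise .001. TFCE power itself cannot be computed from the documents.

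**The case against.** The strongest reply is that section 15.1 never says TFCE-corrected p-values are judged at .001. If .001 is a voxelwise level and the family-wise decision is at .05, step 4 applies and the noise hardly matters. This stands as a condition on the point. It does not remove it, because .001 is the only imaging level the plan states. If .001 is not the decision level, the plan gives none.

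The affected band is also narrow. A true p of .0003 is declared 98% of the time and a true p of .002 only 3% of the time. This stands as well: clear results in either direction are safe.

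A reader might infer that too few permutations inflate false positives. They do not. A random-permutation test that counts the observed labelling keeps its level whatever the number of permutations; what suffers is repeatability near the threshold.

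A reader might also infer that section 15.2 conceals a flaw, or that the basis of the power figure contributes to the seed dependence. Neither is supported. Section 15.2 calls its figure a voxel difference and concedes that brain-wise correction makes such calculations difficult, and the basis of a power calculation has no bearing on Monte Carlo error. The two points are independent, and the power point is one of labelling.

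**Conclusion.** The point holds as a low-cost improvement. If .001 is the level at which permutation p-values are judged, 5000 permutations leave results with a true p of about .0005 to .002 partly to the seed: 28% missed at .0007 and 22% declared at .0013, against about 1% and 2% with 50,000. This rests on binomial sampling of permutations and on reading .001 as the decision level, which is the plain reading but not the only one. Under a family-wise .05 decision the concern is small. The validity of the test is not in question.

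The .07 in section 15.2 is best read as single-voxel sensitivity at alpha .001. The documents do not support a claim that the imaging analysis is underpowered, since neither the within-subject correlation nor the TFCE null distribution is available.

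**What to change.** In section 15.1:
- State whether .001 is a voxelwise level or the TFCE family-wise-corrected level. If it is voxelwise, give the family-wise level at which TFCE results are declared.
- Wherever .001 is the decision level, use at least 50,000 permutations or a tail approximation to the permutation distribution. Recording the seed is good practice and makes a run repeatable, but it does not reduce the Monte Carlo error.

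In section 15.2:
- Label the eta-squared of .07 at alpha .001 as single-voxel sensitivity without brain-wise correction, not as power for the TFCE test.

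The cost is computing time, roughly ten times as many permutations per contrast (50,000/5000 = 10), and a few sentences. Recruitment, visits and sample size are unaffected.
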